2.0 GI Toxicities	
2.2 Hepatitis	

Definition: A disorder characterized by a viral pathologic process involving the liver parenchyma
 
Diagnostic work-up
 
Monitor patient for abnormal liver blood tests: AST, ALT, and bilirubin prior to each infusion and/or weekly if G1 liver function test elevations. No treatment is recommended for G1 liver function test abnormality
 
For G2 or higher:
 
Work-up for other causes of elevated liver enzymes should be tested, viral hepatitis, alcohol history, iron study, thromboembolic event, liver ultrasound, cross-sectional imaging for potential liver metastasis from primary malignancy. If suspicion for primary autoimmune hepatitis is high, can consider ANAs, antismooth muscle antibodies, antineutrophil cytoplasmic antibodies. If patients with elevated alkaline phosphatase alone, g-glutamyl transferase should be tested. For isolated elevation of transaminases, consider checking CK for other etiologies
	
Grading	Management
All patients	
Counsel all patients to be aware of and inform their health care provider immediately if they experience:
 
Yellowing of skin or whites of the eyes Severe nausea or vomiting
 
Pain on the right side of the abdomen Drowsiness
 
Dark urine (tea colored)
 
Bleeding or bruising more easily than normal Feeling less hungry than usual

G1: Asymptomatic (AST or ALT > ULN to 3.0 x ULN and/or total bilirubin > ULN to 1.5 x ULN)	
Continue ICPI with close monitoring; consider alternate etiologies
 
Monitor laboratories one to two times weekly
 
Manage with supportive care for symptom control

G2: Asymptomatic (AST or ALT > 3.0 to ≤ 5 x ULN and/or total bilirubin > 1.5 to ≤ 3 x ULN)	
Hold ICPI temporarily and resume if recover to G1 or less on prednisone ≤ 10 mg/d
 
For Grade 2 hepatic toxicity with symptoms, may administer corticosteroid 0.5-1 mg/kg/d prednisone or equivalent if the abnormal elevation persists with significant clinical symptoms in 3-5 days Increase frequency of monitoring to every 3 days
 
Infliximab might not be the most appropriate treatment option in the situation of immune-mediated hepatitis given the potential risk of idiosyncratic liver failure (Note: No clear evidence shows the liver toxicity from infliximab from other studies)
 
In follow-up, may resume ICPI treatment followed by taper only when symptoms improve to G1 or less and corticosteroid ≤ 10 mg/d; taper over at least 1 month
 
Patients should be advised to stop unnecessary medications and any known hepatotoxic drugs

G3: Symptomatic liver dysfunction, fibrosis by biopsy, compensated cirrhosis, reactivation of chronic hepatitis (AST or ALT 5-20 x ULN and/or total bilirubin 3-10x3 ULN)	
Permanently discontinue ICPI
 
Immediately start corticosteroid 1-2 mg/kg methylprednisolone or equivalent
 
If corticosteroid refractory or no improvement after 3 days, consider mycophenolate mofetil or azathioprine (if using azathioprine should test for thiopurine methyltransferase deficiency)
 
Laboratories at daily or every other day; consider inpatient monitoring for patients with AST/ALT > 8 x ULN and/or elevated TB 3 x ULN
 
Increase frequency of monitoring to every 1-2 days

2.0 GI Toxicities	
	
Infliximab might not be the most appropriate treatment option in the situation of immune-mediated hepatitis given the potential risk of liver failure (Note: No clear evidence shows that the liver toxicity from infliximab from other studies); alternatives include non-TNF-α agents as systemic immunosuppressants. If no improvement is achieved with corticosteroids or for patients on combination therapy with a novel agent, with standard chemotherapy, or with targeted therapy, refer to hepatologist for further pathologic evaluation of hepatitis.
 
Corticosteroid taper can be attempted around 4-6 weeks; re-escalate if needed; optimal duration unclear.

G4: Decompensated liver function (e.g., ascites, coagulopathy, encephalopathy, coma; AST or ALT > 20 x ULN and/or total bilirubin > 10 x ULN)	
Permanently discontinue ICPI
 
Administer 2 mg/kg/d methylprednisolone equivalents
 
If corticosteroid refractory or no improvement after 3 days, consider mycophenolate mofetil
 
Monitor laboratories daily; consider inpatient monitoring
 
Avoid the use of infliximab in the situation of immune-mediated hepatitis
 
Hepatology consult if no improvement was achieved with corticosteroid
 
Corticosteroid taper can be attempted around 4-6 weeks when symptoms improve to G1 or less; re-escalate if needed; optimal duration unclear
 
Consider transfer to tertiary care facility if necessary

All recommendations are expert consensus based, with benefits outweighing harms, and strength of recommendations is moderate.
	

*not approved in Japan.

Abbreviations: ADL, activities of daily living; ALT, alanine aminotransferase; ANA, antinuclear antibody; AST, aspartate aminotransferase; CBC, complete blood count, CK, creatine kinase; CMV, cytomegalovirus; CRP, C-reactive protein; CT, computed tomography; CTCAE, Common Terminology Criteria for Adverse Events; CTLA-4, cytotoxic T-cell lymphocyte-4; EGD, esophagogastroduodenoscopy; ESR, erythrocyte sedimentation rate; G, Grade; GI, gastrointestinal; HIV, human immunodeficiency virus; ICPI, immune checkpoint inhibitor; irAE, immune-related adverse event; IV, intravenous; PD-1; programmed death 1; PD-L1, programmed death ligand 1; TB, tuberculosis; TNF, tumor necrosis factor; TSH, thyroid-stimulating hormone; ULN, upper limit of normal.

Table A3 Management of Lung irAEs in Patients Treated With ICPis

3.0 Lung Toxicities	
3.1 Pneumonitis	

Definition: Focal or diffuse inflammation of the lung parenchyma (typically identified on CT imaging) No symptomatic, pathologic, or radiographic features are pathognomonic for pneumonitis Diagnostic work-up Should include the following: CXR, CT, pulse oximetry For G2 or higher, may include the following infectious work-up: nasal swab, sputum culture and sensitivity, blood culture and sensitivity, urine culture and sensitivity
	
Grading	Management
G1: Asymptomatic, confined to one lobe of the lung or < 25% of lung parenchyma, clinical or diagnostic observations only	
Continue ICPi If clinically indicated. Monitor participants weekly or more frequently as needed with history, physical examination and pulse oximetry; may also offer CXR. May offer one repeat CT scan in 3-4 weeks; in patients who have had baseline testing, may offer a repeat spirometry/DLCO in 3-4 weeks If symptoms appear and/or changes in the physical exam are noted, treat as G2

G2: Symptomatic, involves more than one lobe of the lung or 25%-50% of lung parenchyma, medical intervention indicated, limiting instrumental ADL	
Hold ICPi until resolution to G1 or less Prednisone 1-2 mg/kg/d and taper by 5-10 mg/wk over 4-6 weeks Consider bronchoscopy with BAL Consider empirical antibiotics Monitor every 3 days with history and physical examination and pulse oximetry, consider CXR; no clinical improvement after 48-72 hours of prednisone, treat as G3

G3: Severe symptoms, hospitalization required, involves all lung lobes or 50% of lung parenchyma, limiting self-care ADL, oxygen indicated G4: Life-threatening respiratory compromise, urgent intervention indicated (intubation)	
Permanently discontinue ICPi Empirical antibiotics; (methyl)prednisolone IV 1-2 mg/kg/d; no improvement after 48 hours, may add infliximab 5 mg/kg or mycophenolate mofetil IV 1 g twice a day or IVIG for 5 days or cyclophosphamide; taper corticosteroids over 4-6 weeks Pulmonary and infectious disease consults if necessary Bronchoscopy with BAL ± transbronchial biopsy Patients should be hospitalized for further management


Additional considerations GI and Pneumocystis prophylaxis with PPI and Bactrim may be offered to patients on prolonged corticosteroid use (> 12 weeks), according to institutional guidelines Consider calcium and vitamin D supplementation with prolonged corticosteroid use The role of prophylactic fluconazole with prolonged corticosteroid use (> 12 weeks) remains unclear, and physicians should proceed according to institutional guidelines Bronchoscopy + biopsy; if clinical picture is consistent with pneumonitis, no need for biopsy All recommendations are expert consensus based, with benefits outweighing harms, and strength of recommendations are moderate.
	

Abbreviations: ADL, activities of daily living; BAL, bronchoalveolar lavage; CT, computed tomography; CXR, chest x-ray; DLCO, diffusing capacity of lung for carbon monoxide; G, Grade; GI, gastrointestinal; ICPi, immune checkpoint inhibitor; irAE, immune-related adverse event; IV, intravenous; IVIG, intravenous immunoglobulin; PPI, proton pump inhibitor.

Table A4 Management of Endocrine irAEs in Patients Treated With ICPis

4.0 Endocrine Toxicity	
Counsel patients to inform their health care provider immediately if they experience any changes in their health since their last visit, especially any of the following:	
Headaches that will not go away or unusual headache patterns Vision changes Rapid heartbeat Increased sweating Extreme tiredness or weakness Muscle aches Weight gain or weight loss Dizziness or fainting Feeling more hungry or thirsty than usual Hair loss Changes in mood or behavior, such as decreased sex drive, irritability, or forgetfulness Feeling cold Constipation Voice gets deeper Urinating more often than usual Nausea or vomiting Abdominal pain	
4.1 Thyroid	
4.1.1 Primary hypothyroidism	
Definition: Elevated TSH, normal or low FT4 Diagnostic work-up TSH and FT4 every 4-6 weeks as part of routine clinical monitoring on therapy or for case detection in symptomatic patients	
Grading	Management
G1: TSH < 10 mIU/L and asymptomatic G2: Moderate symptoms; able to perform ADL; TSH persistently > 10 mIU/L	Should continue ICPi with close follow-up and monitoring of TSH, FT4 May hold ICPi until symptoms resolve to baseline Consider endocrine consultation Prescribe thyroid hormone supplementation in symptomatic patients with any degree of TSH elevation or in asymptomatic patients with TSH levels that persist > 10 mIU/L (measured 4 weeks apart) Monitor TSH every 6-8 weeks while titrating hormone replacement to normal TSH FT4 can be used in the short-term (2 weeks) to ensure adequacy of therapy in those with frank hypothyroidism where the FT4 was initially low Once adequately treated, should monitor thyroid function (at least TSH) every 6 weeks while on active ICPi therapy or as needed for symptoms to ensure appropriate replacement; repeat testing annually or as indicated by symptoms once stable
G3-4: Severe symptoms, medically significant or life-threatening consequences, unable to perform ADL	Hold ICPi until symptoms resolve to baseline with appropriate supplementation Endocrine consultation

4.0 Endocrine Toxicity	
	May admit for IV therapy if signs of myxedema (bradycardia, hypothermia) Thyroid supplementation and reassessment as in G2

Additional considerations
 
For patients without risk factors, full replacement can be estimated with an ideal body weight–based dose of approximately 1.6 µg/kg/d
 
For elderly or fragile patients with multiple comorbidities, consider titrating up from low dose, starting at 25-50 mg
 
Extreme elevations of TSH can be seen in the recovery phase of thyroiditis and can be watched in asymptomatic patients to determine whether there is recovery to normal within 3-4 weeks
 
Under guidance of endocrinology, consider tapering hormone replacement and retesting in patients with a history of thyroiditis (initial thyrotoxic phase)
 
Adrenal dysfunction, if present, must always be replaced before thyroid hormone therapy is initiated
	

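### In Appendix 5, Table A4, two consecutive lines on thyroid replacement contradict each other: the low starting dose (25-50 mg) is a few hundred times the full dose (1.6 µg/kg/d)

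*Protocol*

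**What the plan says.** Appendix 5 of the protocol gives investigators recommendations for managing immune-related adverse events, and Section 6.9.2 refers them to its tables for organ-specific management. In Table A4, block 4.1.1 (primary hypothyroidism), the management cell says when to treat: "Prescribe thyroid hormone supplementation in symptomatic patients with any degree of TSH elevation", and also when TSH stays raised without symptoms.

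The additional considerations at the end of that block then give two dose figures, one line after the other:

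- For patients without risk factors: "full replacement can be estimated with an ideal body weight–based dose of approximately 1.6 µg/kg/d".
- For the older or frailer group: "For elderly or fragile patients with multiple comorbidities, consider titrating up from low dose, starting at 25-50 mg".

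The second line names no product and no dosing frequency. Neither the protocol nor the SAP restates or corrects either figure.

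**The concern.** Both lines are about the same treatment in the same cell, and the second is meant to be the cautious version of the first. Its unit is 1,000 times larger, and the comparison comes out the wrong way round: the dose described as low exceeds the dose described as full.

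The stake is participant safety. Thyroid disorders are listed among the important identified risks (Protocol Sections 2.3 and 6.9.2). Free T4 and TSH are tested every 6 weeks (Table 1), so cases will be looked for and treated. The conflicting line concerns older patients and those with several comorbidities. Such patients are expected: inclusion criterion 1 sets no upper age limit, and the SAP plans a subgroup aged 65 or over (Section 8.2) and reporting categories of 75-84 and 85 or over (Section 11.1).

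**Working it through.** The plan has no derived figure to reproduce here. The check is unit arithmetic on the two printed lines.

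**Inputs**

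- Full dose: 1.6 µg/kg/d (Table A4, 4.1.1).
- Starting dose: 25 to 50 mg (same block, next line).
- Ideal body weight: not given in the documents; assumed 40 to 100 kg.
- Frequency of the starting dose: not given; assumed daily.

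**Formulas**

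- Starting dose in micrograms: 25 × 1,000 = 25,000 µg; 50 × 1,000 = 50,000 µg.
- Full dose (µg/d) = 1.6 × ideal body weight (kg).
- Ratio = starting dose ÷ full dose.

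**Results**

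| Ideal body weight (kg) | Full dose (µg/d) | 25 mg ÷ full dose | 50 mg ÷ full dose |
|---|---|---|---|
| 40 | 64 | 391 | 781 |
| 50 | 80 | 312.5 | 625 |
| 60 | 96 | 260 | 521 |
| 70 | 112 | 223 | 446 |
| 80 | 128 | 195 | 391 |
| 90 | 144 | 174 | 347 |
| 100 | 160 | 156 | 312.5 |

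**Does either assumption drive the result?**

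- Weight: the starting dose would equal the full dose only at 25,000 ÷ 1.6 = 15,625 kg, or 50,000 ÷ 1.6 = 31,250 kg. No human weight removes the conflict.
- Frequency: read as a weekly dose, the ratio would still be 156 ÷ 7 ≈ 22 to 781 ÷ 7 ≈ 112. To average out at the full daily dose, it would have to be given once every 156 to 781 days.

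The contradiction therefore does not depend on either assumption; only its size does.

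**The case against.** **It may be a reading artefact.** Only machine-read text was available, and Greek letters are rendered unevenly across Appendix 5. A Latin b stands for beta in the hyperthyroidism block, while the beta is intact under myasthenia gravis. A Latin a stands for alpha under inflammatory arthritis, while the alpha is intact under colitis and hepatitis. The microgram sign survives in the line directly above the disputed one, but since other symbols survive in one place and fail in another, that does not settle the matter. This objection stands to the extent that the original PDF must be checked before the point is sent.

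**The text is guidance.** Appendix 5 offers recommendations, the line asks the prescriber to consider titration, and Section 6.9.2 also points to the current NCCN guideline. The hypothyroidism block adds TSH monitoring during titration and endocrine consultation for grades 3-4. A low dose hundreds of times the full dose one line earlier is also conspicuous, and the documents do not show that any site has copied it. All of this makes harm less likely. It does not make the two lines agree, and at grade 2 specialist consultation is only something to consider.

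**The programme is being wound down.** SAP Section 6.1 restricts the analyses. It does not say that treatment has stopped, so the table may still apply to anyone on study drug.

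**A stronger reading is tempting.** A reader might infer that the milligram line is the wrong one, that a lost Greek letter is the cause, and that changing one unit cures it. The documents do not establish any of these. They show two lines that conflict, without saying which is right or how the conflict arose.

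**Conclusion.** The two lines contradict each other as they stand. With the starting dose taken as daily and ideal body weight as 40 to 100 kg, both of them assumptions, the low dose is about 156 to 781 times the full dose, and about 260 to 520 times at 60 kg. The size moves with the assumptions; the contradiction does not.

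The conclusion is conditional on the original PDF showing the same text. It goes no further than saying that the lines must be reconciled, and takes no position on which dose or unit is correct. Nor should it be read as showing that the protocol orders sites to give 25-50 mg: the text is recommended guidance. No endpoint, sample size or planned analysis is affected. The point merits correction because it is a dose figure in a safety-management table to which the protocol sends its investigators.

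**What to change.** 1. Confirm the wording and units of both lines in the original protocol PDF.
2. If the text is confirmed, reconcile the two lines and their units against the guideline from which Table A4 was taken. State the dosing frequency of the starting dose, which is missing at present.
3. Send the reconciled block to sites.
4. Check the rest of Appendix 5 for similar unit or symbol inconsistencies. One candidate is Table A8, block 8.6, which starts its grading of immune thrombocytopenia at a platelet count below 100/µL. Inclusion criterion 7a requires at least 100 × 10⁹/L, which is 100,000/µL. That is also a 1,000-fold difference, and there the micro sign is intact. Those passages need reconciling too.

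The cost is small: the correction of one table cell, a letter to sites, and a read-through of one appendix.

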4.1.2 Hyperthyroidism	

Definition: Suppressed TSH and high normal or elevated FT4 and/or triiodothyronine
 
Diagnostic work-up
 
Monitor TSH, FT4 every 4-6 weeks from the start of therapy or as needed for case detection in symptomatic patients
 
Consider TSH receptor antibodies if there are clinical features and suspicion of Grave disease (e.g., ophthalmopathy)
 
Close monitoring of thyroid function every 2-3 weeks after diagnosis to catch transition to hypothyroidism in patients with thyroiditis and hyperthyroidism
	
Grading	Management
G1: Asymptomatic or mild symptoms	
Can continue ICPI with close follow-up and monitoring of TSH, FT4 every 2-3 weeks until it is clear whether there will be persistent hyperthyroidism (see below) or hypothyroidism (see 4.1.1)
 
Consider holding ICPI until symptoms return to baseline
 
Consider endocrine consultation
 
b-Blocker (e.g., atenolol, propranolol) for symptomatic relief
 
Hydration and supportive care
 
Corticosteroids are not usually required to shorten duration
 
For persistent hyperthyroidism (> 6 weeks) or clinical suspicion, work-up for Graves disease (TSI or TRAb) and consider thionamide (methimazole or PTU) Refer to endocrinology for Graves disease

G3-4: Severe symptoms, medically significant or life-threatening consequences, unable to perform ADL	
Hold ICPI until symptoms resolve to baseline with appropriate therapy
 
Endocrine consultation
 
b-Blocker (e.g., atenolol, propranolol) for symptomatic relief
 
For severe symptoms or concern for thyroid storm, hospitalize patient and initiate prednisone 1-2 mg/kg/d or equivalent tapered over 1-2 weeks; consider also use of SSKI or thionamide (methimazole or PTU).

Additional considerations
 
Thyroiditis is transient and resolves in a couple of weeks to primary hypothyroidism or normal. Hypothyroidism can be treated as above. Graves' disease is generally persistent and is due to increased thyroid hormone production that can be treated with antithyroid medical therapy. Physical examination findings of ophthalmopathy or thyroid bruit are diagnostic of Graves and should prompt early endocrine referral.
	

4.0 Endocrine Toxicity	
4.2 Adrenal – primary adrenal insufficiency	
Definition: Adrenal gland failure leading to low morning cortisol, high morning ACTH, as well as hyponatremia and hyperkalemia with orthostasis and volume depletion due to loss of aldosterone	

Diagnostic work-up for patients in whom adrenal insufficiency is suspected: Evaluate ACTH (AM), cortisol level (AM) Basic metabolic panel (Na, K, CO₂, glucose) Consider ACTH stimulation test for indeterminate results
 
If primary adrenal insufficiency (high ACTH, low cortisol) is found biochemically: Evaluate for precipitating cause of crisis such as infection Perform an adrenal CT for metastasis/hemorrhage
	
Grading	Management
G1: Asymptomatic or mild symptoms	
Consider holding ICPI until patient is stabilized on replacement hormone
 
Endocrine consultation
 
Replacement therapy with prednisone (5-10 mg daily) or hydrocortisone (10-20 mg orally every morning, 5-10 mg orally in early afternoon)
 
May require fludrocortisone (0.1 mg/d) for mineralocorticoid replacement in primary adrenal insufficiency
 
Titrate dose up or down as symptoms dictate

G2: Moderate symptoms, able to perform ADL	
Consider holding ICPI until patient is stabilized on replacement hormone
 
Endocrine consultation
 
Initiate outpatient treatment at two to three times maintenance (if prednisone, 20 mg daily; if hydrocortisone, 20-30 mg in the morning, and 10-20 mg in the afternoon) to manage acute symptoms.
 
Taper stress-dose corticosteroids down to maintenance doses over 5-10 days
 
Maintenance therapy as in G1.

G3-4: Severe symptoms, medically significant or life-threatening consequences, unable to perform ADL	
Hold ICPI until patient is stabilized on replacement hormone
 
Endocrine consultation
 
See in clinic or, for after hours, make an emergency department referral for normal saline (at least 2 L) and IV stress-dose corticosteroids on presentation hydrocortisone 100 mg or dexamethasone 4 mg (if the diagnosis is not clear and stimulation testing will be needed)
 
Taper stress-dose corticosteroids down to maintenance doses over 7-14 days after discharge
 
Maintenance therapy as in G1

Additional considerations
 
Primary and secondary adrenal insufficiency can be distinguished by the relationship between ACTH and cortisol. If the ACTH is low with low cortisol, then management is as per 4.3.
	

4.0 Endocrine Toxicity	

Patients on corticosteroids for management of other conditions will have low morning cortisol as a result of iatrogenic, secondary adrenal insufficiency. ACTH will also be low in these patients. A diagnosis of adrenal insufficiency is challenging to make in these situations (see next section on hypophysitis).
 
Emergent therapy for someone with suspected adrenal insufficiency is best done with dexamethasone as a stimulation test can still be performed. If the diagnosis is already confirmed, can use hydrocortisone 100 mg.
 
All patients need education on stress dosing and a medical alert bracelet for adrenal insufficiency to trigger stress-dose corticosteroids by EMS.
 
Endocrine consultation prior to surgery or any procedure for stress-dose planning.
	
4.3 Pituitary - hypophysitis	

Definition: Inflammation of the pituitary with varying effects on hormone function. Most commonly presenting with central adrenal insufficiency. May also have central hypothyroidism, diabetes insipidus, and hypogonadism.
 
Diagnostic work-up
 
Diagnosis: Low ACTH with a low cortisol. Low or normal TSH with a low FT4. Hypernatremia and volume depletion with diabetes insipidus. Low testosterone or estradiol with low LH and FSH.
 
Testing:
 
Evaluate ACTH, cortisol (AM), TSH, FT4, electrolytes
 
Consider evaluating LH, FSH, and testosterone levels in males or estrogen in premenopausal females with fatigue, loss of libido, and mood changes Consider MRI of the brain with or without contrast with pituitary/sellar cuts in patients with multiple endocrine abnormalities ± new severe headaches or complaints of vision changes
	
Grading	Management
G1: Asymptomatic or mild symptoms	
Consider holding ICPi until patient is stabilized on replacement hormones
 
Endocrine consultation
 
Hormonal supplementation as in G1

G3-4: Severe symptoms, medically significant or life-threatening consequences, unable to perform ADL	
Hold ICPi until patient is stabilized on replacement hormones
 
Endocrine consultation
 
Hormonal supplementation as in G1
 
Consider initial pulse dose therapy with prednisone 1-2 mg/kg oral daily (or equivalent) tapered over at least 1-2 weeks

Additional considerations
 
Be aware of the need to start corticosteroids first when planning hormone replacement therapy for multiple deficiencies
 
All patients need instruction on doubling doses for illness (stress dosing) and a medical alert bracelet for adrenal insufficiency to trigger stress-dose corticosteroids by EMS
 
Corticosteroid use can cause isolated central adrenal insufficiency
 
Work-up cannot be done with a simple AM cortisol in a patient on corticosteroids for other conditions
 
Laboratory confirmation of adrenal insufficiency should not be attempted until treatment with corticosteroids for other disease is ready to be discontinued. For long-term exposure, consult endocrinology for recovery and weaning protocol using hydrocortisone.
	
